5.5 Secondary endpoints

We will compare changes between the immediate and delayed group from data collected at screening or baseline and weeks 48 and 96.

% change from baseline in BMD at lumbar spine at 96 weeks

% change from baseline in BMD at hip at 48 weeks

% change from baseline in BMD at hip at 96 weeks

Changes in Bone architecture as determined by Trabecular bone scan (TBS)²⁵ and HRpQCT²⁶

Changes in 10 year fracture risk determined by country specific FRAX calculator³³

% with undetectable viral load HIV-1 RNA as per current assays. (This **may be** < 50/ml, < 40/ml or viral load not detected)

Change from baseline in geriatric functional measures: frailty, performance and balance

Change from baseline in muscle quality: Sarcopenia – grip strength measured by a Dynamometer and fat free mass measure (from the DXA)

Change from baseline in lipid values and Framingham cardiovascular risk scores

Changes in renal tubular and glomerular function: eGFR, Cr, urine alb/cr and protein/cr, glucosuria

Safety (clinical and laboratory adverse events)

Changes in biomarkers of inflammation, coagulation and bone metabolism

Tolerability (EuroQoL questionnaire)

5.6 Justification of Endpoints:

Primary Endpoint: BMD assessment with dual energy x-ray absorptiometry (DXA) is well established for the diagnosis of osteoporosis and for fracture risk assessment in postmenopausal women⁷. For BMD measurements to be clinically useful, they are expressed in comparison with

established normative databases. BMD is expressed as a numerical value (g/cm²). Change in BMD is considered a valid intermediate end point for efficacy of fracture risk reduction⁷. To inform the site and timing of the primary endpoint, data from studies of bisphosphonates (a major therapy for osteoporosis) was used in which the increase in BMD is greatest at the lumbar spine, with one half of the gain of BMD achieved within 6–12 months followed by a lower increase over subsequent years³⁴

Secondary Endpoints: New imaging modalities are increasingly incorporated into studies of osteoporosis to gain more detailed information on bone strength.

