2. **Biomarkers of immune activation and inflammation** which could include- (CD38+CD8+ and CD4+T cells), inflammatory cytokines (IL-1b, IL-6, MCP-1, TNF), endothelial activation (sICAM-1, sVCAM-1) and the acute phase reactant hsCRP. ³⁹⁻⁴⁰We are currently conducting a systematic review of the published literature to inform the optimal measures... Panels of the most appropriate measures will be conducted at study end.

The second major reported toxicity of TDF is renal insufficiency ⁴²⁻³. As improvements are reported with TAF, **measures of renal glomerular and tubular function** are included as secondary outcomes. TDF has a more favourable lipid profile than TAF, and we will also assess **lipid parameters and cardiovascular risk scores**.

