11. ASSESSMENT OF SAFETY

11.1 Adverse Events (AEs)

Adverse events (AEs) are defined as any untoward medical occurrence in a participant that does not necessarily have a causal relationship with the study medication/intervention. An AE can therefore be any unfavourable and unintended sign (including abnormal laboratory finding), symptom, or disease temporally associated with the use of study drug/intervention, whether or not it is related to the medication/intervention.

Toxicities will be graded on a 4-point scale according to standard guidelines outlined in the “Division of AIDS Table for Grading the Severity of Adult and Pediatric Adverse Events”⁴⁸[Appendix C]. In general, grade 1 and 2 events will not be considered adverse events, but details should be documented in the source documents. Fractures will be considered and captured as an adverse event regardless of grading.

Stable chronic conditions which are present prior to clinical study entry and do not worsen are not considered adverse events and will be accounted for in the participant's medical history.

Participants who have an adverse event should be followed and treated by the site Investigator until the abnormal parameter or symptom has resolved or stabilized. It is up to the clinician to determine that the AE is either resolved or that it has reached a stable state, after which no further follow-up is necessary. There should also be source documentation to support this determination.

Rates of adverse events, serious adverse events and hospitalisations will be compared between the two arms. Specific attention will be paid to HIV RNA (see below), CD4 cell counts, and metabolic parameters such as fasting glucose, and lipid profiles.

The most common adverse reactions of moderate to severe intensity and incidence $\geq 2\%$ in those receiving TAF are headache, fatigue, nasal congestion and diarrhea.

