In the GLMM model of percent change in BMD at the spine, each patient shall contribute two data points: the percent change in BMD at the spine at 48 weeks and the percent change in BMD at the spine at 96 weeks. A variogram will be used to determine the amount of error due to random effects and serial correlation. If random effects are the source of a significant amount of variation, terms for random intercept and random time shall be included in the model. If serial correlation is determined to be the main source of error, a single parameter will be required to model the correlation between the week 48 and week 96 values from a single patient, since there will be only two BMD values per patient after enrolment.

The model shall contain four covariates: (1) treatment arm, (2) a binary indicator for whether or not the data point corresponds to week 96, (3) the interaction between the treatment arm and the 96 week indicator and (4) a binary for country (Canada vs Italy). If sufficient woman are receiving hormone replacement therapy, an additional binary covariate may be included to capture whether or not the woman was receiving hormone replacement therapy at randomization.

The GLMM model can be expressed as follows:

$$Y = \beta_0 + \beta_1 \text{ treatment} + \beta_2 \text{ week 96} + \beta_3 \text{ treatment* week 96} \quad (1)$$

where Y is the percent change in BMD at the spine.

The hypothesis test for the primary analysis is $H_0: \beta_1 = 0$, which corresponds to the primary hypothesis of the effect of switching from TDF to TAF on percent change in BMD at the spine at 48 weeks.

13.3 Secondary analyses:

The secondary endpoints of greatest importance are: the percent change in BMD at the hip at week 48, the percent change in BMD at the hip at week 96, and the percentage change at the spine at week 96. GLMM will be used to estimate the effect of immediate switch to TAF/FTC on these outcomes

The hypothesis test for the secondary analysis is $H_0: \beta_3 = 0$ in model (1) above, which corresponds to the secondary hypothesis of the effect of switching from TDF to TAF on percent change in BMD at the spine at 96 weeks.

A similar model will be fit for the outcome of percent change in the spine. In that model, the hypothesis tests of $H_0: \beta_1 = 0$ and $H_0: \beta_3 = 0$ will both be of interest, corresponding to the secondary hypotheses of the effects of switching from TDF to TAF on percent change in BMD at the hip at 48 and 96 weeks, respectively.

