Interactions terms will be used to determine if the effect of switching from TDF/FTC to TAF/FTC on 48 week endpoints varies between peri and post-menopausal women or according to whether a protease inhibitor is used as the third ARV.

Other secondary endpoints such as the change in TBS at the hip, the proportions of patients with viral load < 50 copies/mL and the mean eGFR at 48 and 96 weeks will be summarized over time by treatment group to provide preliminary information but will not be compared formally to avoid type 1 errors due to multiple comparisons.

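### Section 5.5 promises between-arm comparison of the secondary endpoints, but 13.3 limits most of them to summaries by arm; multiplicity justifies omitting p-values, not the randomised difference and its confidence interval

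*Combined protocol and SAP*

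**What the plan says.** Section 5.5 opens its list of secondary endpoints with a general commitment: "We will compare changes between the immediate and delayed group from data collected at screening or baseline and weeks 48 and 96". The list covers BMD, bone architecture, FRAX, viral load, geriatric and muscle measures, lipids and Framingham score, renal function, safety, biomarkers and tolerability.

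Section 13.3 divides that list. For hip BMD at weeks 48 and 96 and spine BMD at week 96, "GLMM will be used to estimate the effect of immediate switch to TAF/FTC on these outcomes". The rest is handled in one sentence, which begins "Other secondary endpoints such as the change in TBS at the hip, the proportions of patients with viral load < 50 copies/mL", adds mean eGFR, and says that these are to be summarised by arm over time, as preliminary information, but "will not be compared formally to avoid type 1 errors due to multiple comparisons".

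Section 11.1 makes a separate commitment on safety: "Rates of adverse events, serious adverse events and hospitalisations will be compared between the two arms". For other measures it promises less: "Specific attention will be paid to HIV RNA (see below), CD4 cell counts, and metabolic parameters such as fasting glucose, and lipid profiles".

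**The concern.** An analyst who follows 5.5 produces a between-arm comparison for every secondary endpoint. One who follows 13.3 produces two columns of summaries and stops. The reason given in 13.3 does not settle the matter, because control of type 1 error concerns tests. A difference reported with its interval and labelled exploratory claims no significance. For viral suppression, renal function and lipids, the more harmful mistake is to overlook a real difference, and withholding the contrast gives no protection against that.

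The protocol itself gives these endpoints weight. Section 1.3 holds that a BMD gain with no link to clinical outcomes will not be enough to decide who should switch. Section 5.6 includes renal measures because improvement is reported with TAF, and says that "TDF has a more favourable lipid profile than TAF, and we will also assess" lipid parameters and cardiovascular risk scores. If only arm summaries appear, a reader may take two similar suppression percentages as evidence of equal virologic control without seeing how wide a difference the data allow.

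**Working it through.** **Where the sections agree and differ**

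- Hip BMD (weeks 48 and 96) and spine BMD (week 96): 5.5 and 13.3 both compare the arms. There is no conflict.
- TBS, viral suppression, eGFR: 5.5 compares and 13.3 rules out formal comparison. The conflict is direct. 13.3 also summarises mean eGFR, while 5.5 defines the renal endpoint as change.
- Lipids, Framingham score, FRAX and the remaining 5.5 items: 13.3 does not name them. They fall under its rule only because its list is given by example.
- Adverse events, serious adverse events, hospitalisations: 11.1 promises a comparison, and section 13 gives no effect measure, interval or model. 13.3 does not name safety, so this is mainly a missing method.

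**The plan's own figure.** Section 13.1 assumes a 1% difference, SD 2%, 80% power and alpha .05 (taken as two-sided). The normal approximation is n = 2(1.96 + 0.842)² × (2/1)² = 62.8, so 63 per arm. The two-sample t test gives 63.8, so 64 per arm, with power 80.1%. The stated 128 reproduces. It sizes spine BMD only.

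**Is the worry about multiplicity real?** Section 5.5 has 13 lines; removing the three modelled BMD lines leaves 10. With independent tests at .05, the chance of at least one false positive is 1 − 0.95^10 = 0.40 for 10 tests and 1 − 0.95^13 = 0.49 for 13. That supports not testing. It does not bear on reporting intervals.

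**What the intervals would show.** Inputs are 64 per arm (13.1) and, after the 10% dropout in 13.7, 64 × 0.9 = 57.6, about 58 per arm. Suppression rates are assumptions, equal in both arms.

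For suppression, the Newcombe half-width with equal proportions is √[(p − l)² + (u − p)²], where l and u are the Wilson limits for one arm.

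- 61/64 (95.3%): l = 0.871, u = 0.984; √(0.0821² + 0.0308²) = 0.088, or ±8.8 points.
- 63/64 (98.4%): l = 0.917, u = 0.997; √(0.0677² + 0.0129²) = 0.069, or ±6.9 points.
- With 58 per arm: ±9.6 points at 55/58 and ±7.6 at 57/58.

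The simple formula 1.96√[2p(1 − p)/n] gives 7.6 points at 95% and 4.9 at 98% with n = 64. With one to three failures per arm these are too narrow and should not be used.

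For continuous endpoints the half-width is 1.96√(2/n) SD of the change, before any gain from baseline adjustment: 0.35 SD with 64 per arm and 0.36 SD with 58. This holds only for measures taken in everyone. Under 7.3, TBS and HRpQCT are done at selected sites, so their intervals will be wider.

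**Which time point.** Section 8.3 gives all participants TAF/FTC at week 48. Only the week-48 contrast compares TAF with TDF; the week-96 contrast compares immediate with delayed switch.

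**The case against.** The best defence is that 5.5 lists endpoints while 13.3 is the specific analysis rule, so 13.3 governs, and that comparing and not comparing formally can be read together. The trial is sized for spine BMD alone, descriptive reporting of lower-tier endpoints is accepted practice, and 13.3 presents the summaries as preliminary. An interval of ±9 points on suppression is too wide to establish much.

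Much of this stands. Declining to test these endpoints is not an error. But the two sections can be reconciled only if comparing means setting arm summaries side by side, which leaves the difference without a stated uncertainty. The expected imprecision is a reason to print the interval, since it shows what the data cannot exclude.

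A reader might go further and infer that 13.3 forbids any comparison of the arms, or that the trial will yield no estimate of these effects. The text does not support that. It rules out only formal comparison and keeps summaries by arm, from which a crude difference can be taken. It does not say whether those summaries carry SDs or intervals. A reader might also set 11.1 against 13.3 on viral suppression or lipids, but 11.1 promises comparison only of adverse event, serious adverse event and hospitalisation rates and gives HIV RNA and lipids no more than special attention.

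**Conclusion.** The concern holds in a limited form. Sections 5.5 and 13.3 conflict for TBS, viral suppression and eGFR, and for lipids, FRAX and the rest if the examples in 13.3 are read as open-ended. For these endpoints no between-arm difference with its uncertainty is planned, and the stated reason justifies only the absence of p-values. Separately, the comparison promised in 11.1 has no method. The primary analysis and the three modelled BMD endpoints are unaffected.

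With 64 per arm, the interval now left out would be roughly ±9 points for suppression near 95%, ±7 points near 98%, and ±0.35 SD for continuous endpoints measured in everyone. The suppression figures rest on assumed rates that are equal in the two arms, and all the figures widen slightly at 58 per arm. Whether the key secondary BMD tests need an order or adjustment is a separate question, and this conclusion does not depend on it.

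**What to change.** Replace the sentence in 13.3 with text to this effect: for the remaining endpoints in 5.5, the immediate-minus-delayed difference at week 48 is reported with a 95% confidence interval, without p-values and labelled exploratory, using

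- for continuous endpoints, the difference in change from baseline, adjusted for country and baseline value, including change in eGFR as 5.5 defines it;
- for viral suppression, the risk difference with a Newcombe-type interval;
- for adverse events, serious adverse events and hospitalisations, the risk or rate difference with its 95% interval.

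Report week 96 as immediate versus delayed switch. Align 5.5 and 11.1 to the new text. In the same edit, state one definition of suppression for analysis (13.3 uses < 50 copies/mL, 5.5 allows several assay limits) and reconcile the TBS site (13.3 says hip, 5.6 says lumbar spine images).

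No new data, visits or participants are needed. The cost is a protocol amendment, which 15.2 sends to the ethics board of each centre, and some extra table columns. Where there is no true difference, about 1 in 20 unadjusted intervals will exclude zero by chance, so the exploratory label must stay with the results.

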13.4. Interim analysis: no interim analyses are planned

13.5 Feasibility: The number of women on TDF/FTC aged 45-55 at UHN, MLMC, Modena and Milan are 48, 114, 105 and 80 respectively, for a total of 347. We expect that 90% (n=312) will be eligible and of those, that 80% (n=250) women would agree to participate. In addition each of the additional four Canadian sites have agreed to recruit between 5-10 participants. Therefore, it should thus be feasible to recruit the required 128 women within 12 months.

13.6 Timeline: 6 months for start- up and ethics approval, 12 months for enrollment; 24 months for follow-up; 6 months for analysis/write-up

13.7. Loss to follow-up: We expect that 10% of randomized patients will drop out before 48 weeks. Primary analyses will be conducted assuming data are missing at random. Pattern mixture models and selection models will be used as sensitivity analyses to determine the range of possible treatment effects under the assumption of not missing at random.⁵⁰

14.0 Quality control and quality assurance

Checks will be built into the database to alert the data manager to inconsistent data at the time of data entry. Site personnel will then be prompted to double-check the data. Source documentation will not be verified by an on-site monitor visit during the study. It is the responsibility of the Sponsor Investigator with the CIHR Canadian HIV Trials Network Data Management Centre to assure the quality of computerized data for this study.

15. ETHICS AND PROTECTION OF HUMAN PARTICIPANTS

15.1 ICH Guidance E6:

Good Clinical Practice: Consolidating Guideline/ Declaration of Helsinki. The conduct of this study will conform to the International Conference for Harmonization and Good Clinical Practice (ICH-GCP) regulations and guidelines and the current revision of the Declaration of Helsinki.

15.2 Research Ethics Board/ Institutional Review Board

A copy of the protocol (including protocol amendments), all versions of the informed consents, other information to be completed by participants such as questionnaires, and any proposed advertising/ recruitment materials must be reviewed and approved by the REB/IRB of each participating centre prior to implementation of the study. The site investigator will be responsible for obtaining REB/IRB approval of the annual Continuing Review throughout the duration of the study. The site investigator will notify the REB/IRB of violations from the protocol and serious adverse events.

15.3 Informed consent process

All participants will be given detailed oral and written information about the study. Consent forms describing in detail the study medications/intervention(s), study procedures, anticipated benefits and potential risks will be given to each participant and written documentation of informed consent is required prior to starting the study.

Participants must voluntarily sign and date an informed consent document that has been approved by a participating centre's REB/IRB prior to any procedures being done specifically for the trial. Each participant should have sufficient opportunity to discuss the study and consider the information in the consent process prior to agreeing to participate. Participants may withdraw consent at any time during the course of the trial. The informed consent will be signed and dated by the participant, the person who conducted the informed consent discussion and the investigator. The original signed informed consent form will be retained in the participant's study files and a copy will be provided to the subject.

15.4 Subject confidentiality

All participant related information including the CRFs, laboratory samples, evaluation forms, etc. will be kept strictly confidential. All records will be kept in a secure, locked location and only research staff will have access to the records. Participants will be identified only by means of a coded number specific to each participant, and a participant letter code. All computerized databases will identify participants by numeric codes only, and will be password protected. Upon request, clinical information may be reviewed by or released to study monitors, auditors, or regulatory agencies.

15.5 Early Termination of the Protocol

The REB/IRB or other government organizations, as part of their duties to ensure that research participants are protected may discontinue the study at any time. Regulatory authorities and the study Sponsor retain the authority to suspend additional enrollment for the entire study as applicable.

15.6 Record Retention

The Investigator will maintain all study records according to the ICH-GCP and applicable regulatory requirement(s). Records will be retained for 25 years, in accordance with applicable regulatory requirement(s). If the Investigator withdraws from the responsibility of keeping the study records, custody must be transferred to a person willing to accept the responsibility and the Sponsor notified. The Investigator should ensure that no destruction of medical records occurs without the written approval of the Sponsor.

Samples collected and sent to the central laboratory will be retained for 10 years, after which they will be destroyed.

16.0 PROTOCOL DEVIATIONS

No deviations from this protocol will be permitted without the prior written approval of the Sponsor, except when the modification is needed to eliminate an immediate hazard or hazards to participants. Any deviations that may affect a participant's treatment or informed consent, especially those increasing potential risks, must receive prior approval from the REB unless performed to remove an immediate safety risk to the participants. In this case it will be reported to the REB and the Sponsor immediately thereafter. Any departures from the protocol must be documented.

17.0 STUDY CONDUCT AND MONITORING

The study site agrees to allow monitors direct access to the study records and medical records from those participants enrolled in the clinical study as well as drug accountability records. Monitoring for this study will consist of data management review focused on erroneous data, illogical entries, and missing data and central monitoring of clinical and operational data reviewed for outliers and trends. On-site monitoring will be targeted based on results of the data management and central monitoring reviews as necessary.

18.0 DATA MANAGEMENT RESPONSIBILITIES

Instructions concerning the recording of study data on case report forms will be provided by the CIHR Canadian HIV Trials Network. Each study site is responsible for submitting the data in a timely fashion. It is the responsibility of the Data Management Centre to assure the quality of computerized data for this study. This role extends from protocol development to generation of the final study databases.

19.0 SOURCE DOCUMENTS AND ACCESS TO SOURCE DATA DOCUMENTS

Each participating site must maintain appropriate medical and research records for this study and regulatory/ institutional requirements for the protection of confidentiality of study participants. The Principal Investigator is responsible for assuring that the data collected are complete, accurate, and recorded in a timely manner.

Study data will be collected on study specific CRFs. Source documentation should support the data collected on the CRFs. Source documents include all recordings of observations or notations of clinical activities and all reports and records necessary for the evaluation and reconstruction of the clinical trial. Data for CRFs will be collected during participant visits, phone calls with participants and health care providers, completed questionnaires and abstracted from the participant's medical records. It is not acceptable for the CRF to be the only record of participation in the trial.

Clear and detailed instruction explaining CRF completion and where, when and how CRFs are to be sent to the data centre will be included in the study Operations Manual.

